8.3. Vital Signs

Weight, height, body mass index (BMI) and vital signs, including systolic blood pressure, diastolic blood pressure, pulse rate, respiratory rate and body temperature, will be summarized for each treatment group. A statistical description (number of subjects, mean, standard deviation, median, minimum and maximum) of each parameter at baseline will be provided along with the change from baseline at each subsequent visit. A subject-level listing will also be provided.

8.4. Concomitant Medications

The World Health Organization Drug Dictionary (WHODD) will be used to classify prior and concomitant medications by Anatomical Main Group (Anatomical Therapeutic Chemical, ATC, Level 1), Therapeutic Subgroup (ATC Level 2), and preferred term. Prior and concomitant medication usage will be summarized by the number and percentage of subjects receiving each medication by treatment group.

Subject-level listings containing prior and concomitant medications (WHODD coding), and procedures and non-drug therapies (MedDRA coding) will be provided.

8.5. Extent of Exposure

All treated subjects received a single injection. A list of lot numbers used in this study will be provided in the clinical study report.

9. STATISTICAL CONSIDERATIONS

9.1. Baseline

Baseline is defined as the last value recorded for any given parameter prior to study medication injection. If a subject never received a study injection, baseline is defined as the last value recorded prior to study termination.

9.2. Early Termination

If a subject discontinues the study, early termination assessments will be performed according to the protocol. If these assessments occur within the window of a scheduled visit (+3 days for Weeks 4 and 12 and +7 days for Week 24), they will be associated with that visit for the purposes of FAS and mFAS analysis.

9.3. Electronic Device Entries

Section 7.3.7 of the Protocol provides the schedule of electronic diary and questionnaire completion. Weeks are defined as Day -7 through Day -1 (day before treatment) for baseline, Day 1 (day of treatment) through Day 7 for Week 1, Day 8 through Day 14 for Week 2, and so on. If there is more than one response to any parameter during the associated time period (e.g. more than one Pain NRS entry in one day or more than one KOOS-PS entry in one week), the following steps will be taken in the presented order:

1. Weekly or monthly questionnaires that were completed on a day not specified in Section 7.3.7 of the Protocol (due to device error) will not be considered for analysis
2. Any response after the initial response will not be considered for analysis

9.4. Handling of Missing Data

Missing data will not be imputed for the efficacy analyses described in Section 7. A sensitivity analysis will be performed using the last observation carried forward (LOCF) approach to impute missing assessments at Week 24 for weekly Pain NRS, WOMAC Pain, WOMAC Function and PTGA. This will then be followed by the ANCOVA analysis described in Section 7.2. Since single imputation is not necessary for the PPAS with complete data, LOCF analysis will be performed on the FAS and mFAS, and repeated for the OA phenotypes described in Section 7.1.

In addition, a second sensitivity analysis for change from baseline in weekly Pain NRS, WOMAC Pain, WOMAC Function and PTGA will be conducted using MMRM as outlined in Section 7.5.2.

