Additionally, although many clinical trials with IA therapies commonly use IA saline injections as a placebo comparator arm, there has been growing recognition that the administration of IA saline may have a treatment effect. Several meta-analyses quantifying the effect of IA saline injections on patient-reported outcomes (PRO) such as pain, stiffness, and function in OA clinical trials have found statistically and clinically meaningful improvement in PROs up to 6 months after injection (Zhang et al. 2008, Altman et al. 2016, Saltzman et al. 2016). Clinically noticeable improvements after IA saline injections ultimately call into question the use of such injections as a null control group for comparison to investigative trial arms, as saline may significantly impact clinical symptoms. One hypothesis for this mechanism of action is the dilution of inflammatory mediators within the knee, providing relief of perceived pain, function, as well as stiffness (Zhang et al. 2008, Altman et al. 2016, Saltzman et al. 2016). Determining an adequate control to IA saline injection would remain challenging, while it is suggested that a sham group with a simple needle stick into the joint would remedy some concerns for the potential therapeutic effect of IA saline injections (Saltzman et al. 2016).

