5.5 PARTICIPANT WITHDRAWAL OR TERMINATION

5.5.1 REASONS FOR WITHDRAWAL OR TERMINATION

As the study treatment requires only a single injection, best efforts will be made to encourage subjects to attend all follow-up visits. Subjects will be informed that they are free to withdraw

from the study at any time and for any reason. A premature discontinuation from study will occur when a subject who signed informed consent ceases participation in this study, regardless of circumstances, prior to completion of the defined study period. Subjects can be prematurely discontinued from the study for one of the following reasons:

- Death
- Lost to follow-up after a minimum of 3 attempts have been made to contact the subject, including sending a registered letter
- Subject withdraws consent
- TEAE
- Subject non-compliance
- Request by regulatory authority
- Study terminated by Sponsor

The Investigator may remove a subject from the study if, in the Investigator's opinion, it is not in the best interest of the subject to continue in the study.

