5.2.1. Pain Numeric Rating Scale

The Pain NRS is an 11-point scale (0-10) for subject self-reporting of average knee pain in the last 24 hours, where 0 represents no pain and 10 represents extreme pain. Subjects were prompted to report average pain in the target knee daily on their electronic device (between 5:00 pm and 11:59 pm) from Screening Visit 2 through the end of the study. An average weekly score (referred to as weekly Pain NRS) was calculated for each subject if they had provided a response for at least 4 out of 7 days in a given week. Weeks are defined as Day -7 through Day -1 (day before treatment) for baseline, Day 1 (day of treatment) through Day 7 for Week 1, Day 8 through Day 14 for Week 2, and so on.

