6.3. Per-Protocol Analysis Set

The Per-Protocol Analysis Set (PPAS) includes mFAS subjects who completed the study and did not have any major protocol deviations (see Section 11).

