7.5.2. Mixed-Effects Model for Repeated Measures

Change over time in primary and secondary endpoints (weekly Pain NRS, WOMAC Pain, WOMAC Function and PTGA) as well as weekly measures (KOOS-PS and NSAID usage) will be characterized using mixed-effects models for repeated measures (MMRM). The models will estimate change from baseline with treatment, week, treatment×week interaction and baseline value as covariates.

For weekly measured outcomes, MMRM will be estimated assuming a Toeplitz variance-covariance matrix. The Toeplitz structure is a more generalized form of autogressive-1 (AR1) structure, allowing the data to inform how the correlation between within-subject observations decreases over time instead of implicitly defining a uniform decay structure. For monthly measured outcomes, MMRM will be estimated assuming an unstructured variance-covariance matrix, allowing the data to fully inform the correlation between within-subject observations. (Kincaid 2005)

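### The observed-case ANCOVA, LOCF and MMRM planned for Week 24 cannot show whether subjects who left did worse, so agreement among them would not establish robustness to dropout

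*SAP*

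**What the plan says.** SAP 9.4 sets the main rule: "Missing data will not be imputed for the efficacy analyses described in Section 7". The Week 24 ANCOVA of SAP 7.2 and 7.3 therefore uses only subjects with a Week 24 value.

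The same section then plans two sensitivity analyses.

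- The first: "A sensitivity analysis will be performed using the last observation carried forward (LOCF) approach to impute missing assessments at Week 24". It covers weekly Pain NRS, WOMAC Pain, WOMAC Function and PTGA, uses the SAP 7.2 ANCOVA, and is run in the FAS and mFAS and in the phenotype populations of SAP 7.1.
- The second: "a second sensitivity analysis for change from baseline in weekly Pain NRS, WOMAC Pain, WOMAC Function and PTGA will be conducted using MMRM". Of this model SAP 7.5.2 says: "The models will estimate change from baseline with treatment, week"; a treatment-by-week interaction and the baseline value complete the list of terms.

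No delta-adjusted, tipping-point, reference-based or other missing-not-at-random analysis appears in either document. The fourth primary endpoint, mJSW, is in neither sensitivity analysis.

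Treatment is one injection on Day 1. Protocol 5.5.1 says: "As the study treatment requires only a single injection, best efforts will be made to encourage subjects to attend all follow-up visits". Protocol 7.3.5 lists no Pain NRS, WOMAC or PTGA at the early termination visit, where the electronic device is handed back. Patient-reported data therefore stop when a subject leaves.

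**The concern.** A sensitivity analysis for missing data should ask how far the result would move if the main analysis were wrong about the subjects it cannot see. The natural question here is whether those who left had lost their improvement.

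The observed-case ANCOVA in effect assumes that they resemble those who stayed. The MMRM assumes that they resemble those who stayed and had similar earlier scores. LOCF assumes that they stay where they were last seen. For a monthly questionnaire that can be a score from Week 4 to Week 20; for the weekly Pain NRS it can be as late as Week 23. None of these assumptions lets a dropout's Week 24 score be worse than the observed data suggest. If the three analyses agree, a reader may take the result as robust to dropout when that has not been tested.

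LOCF has a further weakness. After a single injection the response may change during 24 weeks, and an earlier score is then not a Week 24 score.

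**Working it through.** **Inputs from the documents.** About 630 subjects in six equal arms (Protocol 10.5): 630/6 = 105 per arm. Unadjusted 95% confidence intervals (SAP 7.2), read here as a two-sided 5% test. No effect size, SD, power or dropout rate is given, so 630 cannot be reproduced. Everything below marked as assumed is illustration.

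**1. Bias of LOCF.** Let p be the share of an arm imputed, c the mean score carried forward for those subjects, and m their true Week 24 mean. Then

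LOCF difference - true difference = p_A(c_A - m_A) - p_V(c_V - m_V).

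The sign is not fixed, because early vehicle response is carried forward too.

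*Early drug effect that has gone.* Assume equal dropout p, a stable vehicle arm, an early effect e (SD units) gone by Week 24, and every dropout last seen while the full early effect was present. The bias is p × e. With SE = √(2/105) = 0.138 SD, the rejection probability when the true difference is zero is Φ(pe/SE - 1.96) + Φ(-pe/SE - 1.96).

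Example: p = 0.20 and e = 0.5 give a bias of 0.10 SD; 0.10/0.138 = 0.72; rejection is 11.2%.

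| Dropout (assumed) | e = 0.3 SD | e = 0.5 SD | e = 0.7 SD |
|---|---|---|---|
| 5% | 5.1% | 5.4% | 5.7% |
| 10% | 5.5% | 6.5% | 8.0% |
| 15% | 6.2% | 8.5% | 11.9% |
| 20% | 7.2% | 11.2% | 17.4% |

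A simulation (six monthly visits, correlation 0.8 to the power of the lag, dropouts last seen at Week 4 or 8, e = 0.5, 3,000 runs) gave LOCF estimates of 0.05 and 0.10 SD and rejection of 7.2% and 10.6% at 10% and 20% dropout. Observed cases and a missing-at-random estimate (arm-specific sequential regression, standing in for the MMRM) were both about 0.

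The bias is smaller when dropout is spread over all visits. In two simulations with SD 20, correlation 0.6 and an early effect of 8 to 12 points, LOCF was off by 1.2 to 1.7 points with 7-12% error at 20% dropout. At 10% dropout it was off by 0.6 to 0.9 points with 5-6% error.

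*No drug effect, unequal dropout.* Assume dropout of 10% and 25%, and a response that fades by 8 points in both arms. The bias is (0.25 - 0.10) × 8 = 1.2 points. Its direction depends on which arm loses more subjects. With SD 20 this is 0.06 SD, and the formula above gives 7.2% error.

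**2. Dropouts who lose their benefit.** Assume a lasting effect of 0.5 SD, lost entirely by active dropouts. The true all-subject difference is 0.5 × (1 - p): 0.45 SD at 10% dropout and 0.40 SD at 20%. In the same type of simulation, observed cases, LOCF and the missing-at-random estimate all returned about 0.50 SD. All three overstate by 0.05 or 0.10 SD, and they agree with each other.

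**3. Dropouts back at baseline, unequal dropout.** Assume, on a 0-100 scale, changes of -25 (active) and -20 (vehicle) at every observed visit, with 20% active and 10% vehicle dropout.

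- All-subject truth: active 0.8 × (-25) + 0.2 × 0 = -20; vehicle 0.9 × (-20) + 0.1 × 0 = -18; difference **-2.0**.
- Observed cases: -25 - (-20) = **-5.0**.
- LOCF: dropouts carry -25 and -20, so again **-5.0**.
- Vehicle-based imputation of active dropouts: 0.8 × (-25) + 0.2 × (-20) = -24, against -20; difference **-4.0**.
- Delta adjustment by arm: -5 + 0.2δ_A - 0.1δ_V. With δ_A = 25 and δ_V = 20 this is -5 + 5 - 2 = **-2.0**.

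Of these options, only the delta adjustment reaches the truth.

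**The case against.** The strongest reply is that a worn-off effect would not go unnoticed. The MMRM has a treatment-by-week term and does not carry an early effect forward. The by-visit ANCOVAs of SAP 7.5.1 and the over-time figures of SAP 7.3 would also show fading. This stands: a reader who infers that LOCF is the only check at Week 24 is mistaken. It does not help with dropouts who did worse, because the MMRM is valid only under missing at random.

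It can also be said that LOCF is supportive and does not drive the primary result, that this is a Phase 2 dose-finding study with unadjusted P values, and that dropout may be low. All of this is fair. At 5% dropout the LOCF error is at most 5.7% under the assumed effects.

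Three stronger readings are tempting, and the documents do not support them.

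- *That the protocol itself shows waning before Week 24.* Protocol 2.2 says of meta-analyses of intra-articular saline that they "have found statistically and clinically meaningful improvement in PROs up to 6 months after injection". That period reaches Week 24 and concerns a comparator. Neither document says that response to SM04690 fades.
- *That LOCF must favour SM04690.* The bias can go either way.
- *That skipping LOCF in the PPAS is an error because its data may be incomplete.* The PPAS "includes mFAS subjects who completed the study and did not have any major protocol deviations", and a weekly Pain NRS exists only "if they had provided a response for at least 4 out of 7 days in a given week". A completer could therefore lack a Week 24 value. Whether such a subject stays in the PPAS depends on whether the gap counts as a major deviation. SAP 11 includes materially reduced completeness of data in that definition and leaves the criteria to a classification guideline that is not among the documents.

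**Conclusion.** The concern holds in a limited form. The plan has no analysis of whether subjects who left did worse than their observed scores suggest, so agreement among observed-case ANCOVA, LOCF and MMRM would not show robustness to dropout. LOCF adds a bias of its own, in either direction, which the MMRM does not share.

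The size cannot be fixed from the documents. Under the assumed early effects of 0.3 to 0.7 SD, LOCF's two-sided error is about 5-6% at 5% dropout, 5.5-8% at 10% and 7-17% at 20%. These figures assume that all dropouts left while the full early effect was present. In the assumed back-at-baseline case the observed-case and LOCF results overstate the all-subject difference by 3 points (-5.0 against -2.0). With little and balanced dropout, both problems are small.

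This is not evidence that the primary result will be wrong. It limits what the trial could claim about robustness, and mJSW has no sensitivity analysis for missing data at all.

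**What to change.** In SAP 9.4:

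1. Replace LOCF with multiple imputation from the collected weekly and monthly scores, by arm, for Pain NRS, WOMAC Pain, WOMAC Function and PTGA.
2. Make a delta-adjusted tipping-point run the core. Add a worsening delta to the imputed Week 24 values, varied separately by arm, from zero up to at least the amount that returns imputed subjects to baseline. Set the grid per scale, since Pain NRS is 0-10 while WOMAC and PTGA are analysed on 0-100. Report the pairs of deltas at which the conclusion changes.
3. Analyse each imputed set with the SAP 7.2 ANCOVA and combine by Rubin's rules, in the FAS and mFAS and in the three phenotype populations.
4. A vehicle-based imputation may be added as one scenario, but it is not sufficient alone: it gives -4.0 where the truth is -2.0 in the example above.
5. Keep the MMRM as planned.
6. Apply the delta-adjusted imputation to mJSW. Radiographs are scheduled only at Screening Visit 1 and at Week 24 or early termination, so the imputation model there rests mainly on baseline mJSW and arm. The delta run then carries most of the weight.

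The cost is SAP text, more programming and more tables. No new data are collected. The sensitivity intervals will be wider than those from LOCF, which treats imputed scores as if they had been observed.

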10. STUDY SUBJECTS

10.1. Disposition of Subjects

Subject disposition will be presented in a summary table detailing the number and percentage of subjects who were consented, randomized, treated, completed the study or discontinued (e.g. screen failure, subject decision, etc.) by treatment group, site and randomization cohort. The disposition for individual subjects will be listed along with additional information on discontinued subjects.

10.2. Demographic and Baseline Characteristics

Demographic and baseline characteristics, including gender, race, ethnicity, age, weight, height, body mass index (BMI), Kellgren-Lawrence (KL) grade, OA laterality, WPI and SSQ2 will be presented by treatment group. Continuous variables will be summarized with descriptive statistics and categorical variables will be summarized with frequencies and percentages. The summaries will be provided for each analysis set and OA phenotype. Subject level listings will also be provided.

10.3. Medical History

Medical history will be collected at screening and reassessed at the Week 24 (EOS) / Early Termination visit to record any changes. A summary of reported medical history will be provided by system category for each treatment group in the SAS. A subject-level listing will provide further information on each event.

11. PROTOCOL DEVIATIONS

A protocol deviation is defined as any change, divergence or departure from the study design or procedures of a research protocol that is under the Investigator's control and that has not been approved by the site's Institutional Review Board (IRB).

Deviations are summarized into one of the following categories:

- Informed Consent
- Enrollment
- Procedures
- Labs/Specimens
- Study Visits
- Source Documentation
- Investigational Product
- Diaries, Questionnaires, or Patient Reported Outcomes
- IXRS (Interactive Response Technologies)
- Subject Non-Compliance
- Adverse Events

Deviations are categorized as major or minor by a cross-functional team according to pre-defined criteria established in the Protocol Deviation Classification Guideline.

- A major deviation is defined as a divergence from the protocol that materially (a) reduces the quality or completeness of the data, (b) makes the informed consent inaccurate, or (c) impacts a subject's safety, rights or welfare.
- A minor deviation is defined as a divergence from the protocol that deviates from the procedures and guidelines outlined in the protocol, but is not classified as a major deviation (i.e. the deviation does not materially (a) reduce the quality or completeness of the data, (b) make the informed consent inaccurate, or (c) impact a subject's safety, rights or welfare).

Protocol deviations will be summarized by site, category and classification, and listed for each subject.

12. ANALYSIS SOFTWARE

All data processing, summarization and analyses will utilize SAS® Version 9.4, equipped with Cytel Inc.'s PROC MCPMOD.

